8.2 ADVERSE EVENTS AND SERIOUS ADVERSE EVENTS

IRBMed's guidelines on adverse events (AE) and serious adverse events (SAE) reporting will be followed. These guidelines include the definitions of AE/SAE and when to report it.

8.3 UNANTICIPATED PROBLEMS

IRBMed's guidelines on unanticipated problems (UaP) reporting will be followed. These guidelines include the definition of UaP and when to report it.

9 STATISTICAL CONSIDERATIONS

9.1 Statistical Hypotheses

- **Primary Efficacy Endpoint:**
- Fluoride concentration in dental biofilm
 - Null hypothesis: A fluoride rinse preceded by a calcium rinse is not superior than a fluoride-only rinse in enhancing fluoride concentration in dental biofilm (fluid and solid phases) up to 2 h after mouth rinsing.
 - Alternative hypothesis: A fluoride rinse preceded by a calcium rinse is superior than a fluoride-only rinse in enhancing fluoride concentration in dental biofilm (fluid and solid phases) up to 2 h after mouth rinsing.
- **Secondary Efficacy Endpoints:**
- Fluoride concentration in saliva
 - Null hypothesis: A fluoride rinse preceded by a calcium rinse is not superior than a fluoride-only rinse in enhancing fluoride concentrations in saliva up to 2 h after mouth rinsing.
 - Alternative hypothesis: A fluoride rinse preceded by a calcium rinse is superior than a fluoride-only rinse in enhancing fluoride concentrations in saliva (fluid and solid phases) up to 2 h after mouth rinsing.
- Calcium concentration in dental biofilm
 - Null hypothesis: A fluoride rinse preceded by a calcium rinse is not superior than a fluoride-only rinse in enhancing calcium concentration in dental biofilm (fluid and solid phases) up to 2 h after mouth rinsing.

- Alternative hypothesis: A fluoride rinse preceded by a calcium rinse is superior than a fluoride-only rinse in enhancing calcium concentration in dental biofilm (fluid and solid phases) up to 2 h after mouth rinsing.
- Calcium concentration in saliva
 - Null hypothesis: A fluoride rinse preceded by a calcium rinse is not superior than a fluoride-only rinse in enhancing calcium concentration in saliva up to 2 h after mouth rinsing.
 - Alternative hypothesis: A fluoride rinse preceded by a calcium rinse is superior than a fluoride-only rinse in enhancing calcium concentration in saliva up to 2 h after mouth rinsing.
- Tertiary/exploratory Endpoints:
- Correlation between salivary flow rate and fluoride concentration in dental biofilm
 - Null hypothesis: There is no correlation ($\beta = 0$) between salivary flow rate and fluoride concentration in dental biofilm after rinsing with a fluoride mouth rinse.
 - Alternative hypothesis: There is a correlation ($\beta \neq 0$) between salivary flow rate and fluoride concentration in dental biofilm after rinsing with a fluoride mouth rinse.
- Correlation between salivary flow rate and fluoride concentration in saliva
 - Null hypothesis: There is no correlation ($\beta = 0$) between salivary flow rate and fluoride concentration in saliva after rinsing with a fluoride mouth rinse.
 - Alternative hypothesis: There is a correlation ($\beta \neq 0$) between salivary flow rate and fluoride concentration in saliva after rinsing with a fluoride mouth rinse.

9.2 SAMPLE SIZE DETERMINATION

Data from Souza et al., 2016, using rinses similar to be used in this study, were used in sample size calculation. In that study, analysis of fluoride concentration in dental biofilm 10 h after using the rinses was available. (Note that the expected differences between the groups up to 2 h after the mouth rinsing are expected to be bigger, as saliva production overtime tends to clear all substances from the mouth).

Considering an 80% power to detect differences at the 5% significance level, an estimated sample size of 15 was determined (Stata/SE 15.1 for Mac). The sample size was increased to 20 subjects considering an attrition of 30%.

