7.2 PARTICIPANT DISCONTINUATION/WITHDRAWAL FROM THE STUDY

Participants are free to withdraw from participation in the study at any time upon request.

An investigator may discontinue or withdraw a participant from the study for the following reasons:

- Significant study intervention non-compliance
- If any clinical unanticipated adverse event (AE) occurs such that continued participation in the study would not be in the best interest of the participant
- Disease progression (oral or general) which requires discontinuation of the study intervention
- If the participant meets an exclusion criterion (either newly developed or not previously recognized) that precludes further study participation

The reason for participant discontinuation or withdrawal from the study will be recorded on the Discontinuation Case Report Form (CRF). Subjects who sign the informed consent form and are randomized but do not receive the study intervention may be replaced. Subjects who sign the informed

consent form, and are randomized and receive the study intervention, and subsequently withdraw, or are withdrawn or discontinued from the study will not be replaced.

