7.3 LOST TO FOLLOW-UP

A participant will be considered lost to follow-up if he or she fails to return for the third study visit (second intervention visit) and is unable to be contacted by the study site staff.

The following actions must be taken if a participant fails to return to the clinic for a required study visit:

- The site will attempt to contact the participant and reschedule the missed visit and counsel the participant on the importance of maintaining the assigned visit schedule and ascertain if the participant wishes to and/or should continue in the study.
- Before a participant is deemed lost to follow-up, the investigator or designee will make every effort to regain contact with the participant (where possible, 3 telephone calls and, if necessary, a certified letter to the participant's last known mailing address or local equivalent methods). These contact attempts should be documented in the participant's medical record or study file.
- Should the participant continue to be unreachable, he or she will be considered to have withdrawn from the study with a primary reason of lost to follow-up.

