9.3 POPULATIONS FOR ANALYSES

For the primary and secondary outcomes, only participants completing the whole study will provide data for the analyses (per-protocol analysis).

For the tertiary outcomes, a modified intention-to-treat analysis will be used; all volunteers completing the fluoride-only mouth rinse treatment will provide data for the correlation analyses, even if they did not complete the other study treatment.

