9.4.2 ANALYSIS OF THE PRIMARY EFFICACY ENDPOINT(S)

Fluoride concentration in dental biofilm (primary efficacy endpoint) will be determined from the samples collected at baseline and 15 min, 60 min and 120 min (± 5 min) after rinsing with the assigned mouth rinse(s). The concentration at each individual timepoint will be compared between the two intervention groups. Also, the area under the curve of fluoride concentration in dental biofilm versus time will be calculated. This single measurement of fluoride bioavailability overtime after the mouth rinse(s) will be compared between the two intervention groups.

Each set of data will be checked for normality of errors. If the data is not normal, it will be log-transformed. An analysis of variance will be conducted, considering as factors the participant (experimental block) and the treatment. The use of the participant as a source of variation aims solely to reduce unknown variability in the error. An alpha level of 5% will be used to determine significant differences between the two groups.

In case data were log-transformed to fit the statistical analysis, their geometric means and confidence intervals (calculated from the log-transformed data) will be presented.

If data is missing from one of the intervention groups, the rest of the participant data (from the other intervention) will be excluded from the analysis.

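### Section 9.2: enrolling 20 to keep 15 allows for 25% attrition, not the stated 30%; a 30% loss without replacement leaves 14 completers

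*Combined protocol and SAP*

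**What the plan says.** Section 9.2 sizes the trial for 80% power at the 5% level and reports that "an estimated sample size of 15 was determined". It continues: "The sample size was increased to 20 subjects considering an attrition of 30" per cent. No other attrition rate and no other method of inflation appears in the document.

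Three other sections bear on how the 15 and the 20 relate:

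- **Who is analysed.** For the primary and secondary outcomes, section 9.3 says that "only participants completing the whole study will provide data for the analyses (per-protocol analysis"). Section 9.4.2 adds that if data from one intervention are missing, "the rest of the participant data (from the other intervention) will be excluded from the analysis".
- **Who is replaced.** Under section 7.2, participants who leave after receiving the study intervention and are "withdrawn or discontinued from the study will not be replaced". Those who are "randomized but do not receive the study intervention may be replaced".
- **Missed visits.** Section 7.3 says: "The site will attempt to contact the participant and reschedule the missed visit".

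**The concern.** An attrition rate is normally read as the share of enrolled participants who do not finish. On that reading, the sentence in 9.2 tells the reader that 30% of the 20 can be lost with the required 15 still in hand. That is not so.

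The attrition allowance is the only reason given for going from 15 to 20, so the plan relies on it. Anyone following losses during the trial would believe that six non-replaced losses are covered, when only five are.

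**Working it through.** **Inputs.** Required number 15, enrolled number 20, attrition 30% (all section 9.2). The primary analysis uses completers only (9.3, 9.4.2), so 15 is the number that must remain after losses.

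**Step 1: reproduce the plan's figure.** Adding 30% to the required number gives 15 × (1 + 0.30) = 19.5, rounded up to **20**. This matches 9.2 exactly. It takes the 30% as a share of those who complete, not of those who enrol.

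**Step 2: what 20 delivers at 30% attrition.** Losses: 20 × 0.30 = 6. Completers: 20 − 6 = **14**, one below 15.

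**Step 3: what attrition 20 covers.** Losses that can be absorbed: 20 − 15 = 5. As a rate: 5/20 = **25%**.

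**Step 4: what 30% would need.** Required number divided by the share retained: 15/(1 − 0.30) = 21.43, rounded up to **22**. Check: 21 × 0.70 = 14.7 (below 15); 22 × 0.70 = 15.4.

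**Step 5: chance of reaching 15.** Assume that each participant is lost independently with probability 0.30 and that nobody is replaced. The binomial probability of at least 15 completers is 42% with 20 enrolled and 67% with 22.

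**Step 6: effect on power, as an illustration.** Section 9.2 gives no effect size, standard deviation or sidedness, so the 15 itself cannot be re-derived. I assume a paired t-test, analysed one-tailed at 5% as in section 9.4.1. The lower end of each range takes 15 as giving exactly 80% power. The upper end is the limit at which 14 would already have given 80%; it is not reached if 15 was the smallest sufficient number.

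| How 15 was sized (assumed) | Standardized effect, lower to upper end | One-tailed power at 14 completers |
|---|---|---|
| One-sided 5% | 0.675 to 0.702 | 77.3% to just under 80% |
| Two-sided 5% | 0.778 to 0.810 | 86.6% to just under 88.9% |

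In the least favourable case, a standardized effect 3.9% larger (0.702/0.675, unrounded ratio 1.039) restores 80% at 14.

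**The case against.** The case for leaving the sentence alone has four parts.

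1. **The 30% may have been meant as an addition to 15.** Section 9.2 does not say what it is a percentage of, and as an addition it yields 20 exactly. This explains how the figure arose. But the sentence calls it attrition, and with a completers-only analysis the relevant rate is the loss from those enrolled.

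2. **The shortfall is conditional.** The schedule of activities (1.3) puts randomization at Visit 1 and the first rinse at Visit 2. Some losses can therefore fall before any rinse, where 7.2 permits replacement. If one of six is replaced by someone who completes, 15 is restored. This stands, and it limits the size of the problem. However, replacement is optional and does not extend to anyone lost after the first rinse, and nothing says that the 30% is net of replacement. Rescheduling under 7.3 may lower the actual loss, but it does not make 20 sufficient for 30%.

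3. **There may be power to spare.** Section 9.2 sized on data from 10 h after rinsing and notes that "the expected differences between the groups up to 2 h after the mouth rinsing are expected to be bigger". A modestly larger effect would offset the loss of one completer. The plan does not quantify this margin, though, and it does not bear on the percentage.

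4. **Restating the allowance as 25% fits the assumption to the sample size.** Nothing in the document shows that 25% is the expected loss. This is a fair point: the choice between restating the allowance and enrolling more belongs to the sponsor, and a restated sentence should disclose what happens at 30%.

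**Conclusion.** The concern holds, as a minor arithmetic error. Given a requirement of 15 completers, 20 enrolled covers 25% attrition and not 30%. That conclusion uses only the plan's own numbers and the ordinary meaning of attrition.

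The practical effect is small or nil: one completer short if all six losses go unreplaced. The power figures are illustrative and rest on the assumed paired design and effect size; they should not be read as the trial's actual power. The analysis is not otherwise affected.

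**What to change.** Keep 20 and replace the attrition sentence in 9.2 with wording such as:

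> Twenty participants will be enrolled. This retains 15 completers if up to 25% (5 of 20) are lost without replacement; at 30% loss without replacement, 14 would complete.

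If the sponsor wants to state the power at 14 completers, it should compute it from its own effect size, standard deviation and sidedness.

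The cost is one sentence, and the stated allowance drops from 30% to 25%. The randomization table of 20 rows with 10 of each letter (6.3), the cap of 10 participants with normal flow (8.1) and the analysis all stay as they are.

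If the sponsor does expect 30% non-replaced loss, the alternative is to enrol 22. That means two more participants and changing the 20 in the synopsis (1.1), the randomization table (6.3) and the screening table and accompanying text (8.1), as well as in 9.2.

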9.3 POPULATIONS FOR ANALYSES

For the primary and secondary outcomes, only participants completing the whole study will provide data for the analyses (per-protocol analysis).

For the tertiary outcomes, a modified intention-to-treat analysis will be used; all volunteers completing the fluoride-only mouth rinse treatment will provide data for the correlation analyses, even if they did not complete the other study treatment.

9.4 STATISTICAL ANALYSES

9.4.1 GENERAL APPROACH

Descriptive statistics: Data of fluoride concentration in saliva and dental biofilm tend to have a not-normal distribution. If that is the case in this study, these data will be presented as the geometric mean

(of log transformed data) and confidence interval (calculated from log transformed data). Data of calcium, if fitting normal distribution, will be presented as means and standard deviations. If not fitting normal distribution, the same approach for fluoride will be used.

Inferential tests: The comparisons between groups will be made using analysis of variance, having the volunteers as statistical blocks (source of variation). This is only to reduce known variability from the error calculation. One-tailed tests will be used to test for superiority of one treatment versus the other. The p-value will be set at 5%.

Before the analysis of variance, the normality of errors will be tested. It is expected that fluoride data is not normally distributed, and therefore a log transformation of data will be performed (which usually is adequate to normalize the data). The same approach will be used for the calcium data.

Besides the groups comparisons, the salivary flow rate will be correlated with the fluoride concentration in dental biofilm and saliva, to help understand the effect of flow rate on fluoride salivary clearance. For that, a regression analysis will be used to correlate the data of salivary flow with fluoride concentration (area under the curve of fluoride concentration over time) in saliva and dental biofilm. A significance level of 5% will be used in this analysis.

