2.2 BACKGROUND

Dry mouth is a serious and prevalent problem in older adults [Furness et al., 2011] and is associated with increased risk for oral diseases, such as caries [Navazesh, 2012]. The lack of saliva reduces the clearance of cariogenic sugars and acids from the dental biofilm, impairs the action of salivary buffering agents and reduces the supply of calcium and phosphate ions, which are natural remineralizing agents [Edgar et al., 2012]. Based on limited evidence, higher fluoride concentration products are usually recommended for older adults with hyposalivation [Zero et al., 2016].

Nevertheless, previous studies have shown that a calcium (Ca) prerinse can boost the retention of F in the mouth [Vogel et al., 2006a; 2006b; 2008a; 2008b; Souza et al., 2016], enhancing its effect. Although the effect of the Ca prerinse on F availability in hyposalivation patients has never been studied, preliminary data give support to the enhanced effect expected for this procedure. Using an in situ model, it was shown that a Ca prerinse used before a F rinse for 14 days increased ~22 and 4-fold the F and Ca concentrations in dental biofilm, respectively [Souza et al., 2016]. This corroborates the hypothesis that the retention of F in the mouth can be enhanced, without the need to increase the F concentration in them. The increased F and Ca retention may be particularly useful for hyposalivation patients.

In the current project we aim to assess the effect of this approach in maintaining increased and sustained levels of Ca and F in the oral fluids of patients with a range of salivary flow rates, varying from normal to hyposalivation. There are no known risks associated with the use of these rinses.

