3 OBJECTIVES AND ENDPOINTS

OBJECTIVES	ENDPOINTS	JUSTIFICATION FOR ENDPOINTS
Primary		
Determine the benefit of using a calcium rinse, before a fluoride rinse, to enhance fluoride retention in dental biofilm of individuals with hyposalivation.	Fluoride concentration in dental biofilm (fluid and solid phase) up to 2 h after rinsing with fluoride.	Dental biofilm can take up fluoride and release it for prolonged periods of time, like the hours in between oral hygiene procedures.
Secondary		

OBJECTIVES	ENDPOINTS	JUSTIFICATION FOR ENDPOINTS

Determine the benefit of using a calcium rinse, before a fluoride rinse, to enhance fluoride retention in saliva of individuals with hyposalivation.
	
 1. Fluoride concentration in saliva up to 2 h after rinsing with fluoride. 2. Calcium concentration in dental biofilm (fluid and solid phase) up to 2 h after rinsing with fluoride. 3. Calcium concentration in saliva up to 2 h after rinsing with fluoride. 	
 1. Salivary fluoride can be considered as a surrogate measure of fluoride availability in the mouth, because from saliva fluoride from rinses gets to dental biofilm. 2. Since a calcium rinse will be used in one of the treatments in this study, determination of calcium concentration in dental biofilm will be made to identify potential sources of fluoride retention (e.g. fluoride bound to calcium ions, calcium fluoride precipitation). 3. Salivary calcium can be considered as a surrogate measure of calcium availability in the mouth; since a calcium rinse will be used in one of the study treatments, salivary calcium will be determined.
Tertiary/Exploratory		

Determine the role of hyposalivation on the retention of fluoride in the mouth after a fluoride rinse
	
 1. Correlation between salivary flow rate and fluoride concentration in dental biofilm up to 2 h after a rinse. 2. Correlation between salivary flow rate and fluoride concentration in saliva up to 2 h after a rinse. 	
The correlation between salivary flow rate and fluoride in dental biofilm and saliva will be investigated to estimate how the flow rate affect these variables.

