4 STUDY DESIGN

4.1 OVERALL DESIGN

The overall hypothesis of this study is that a calcium prerinse used before a fluoride rinse enhances the retention of fluoride in the mouth. Additional hypothesis to be tested is that the reduction in saliva flow (hyposalivation) reduces the clearance and therefore increases the retention of fluoride in the mouth.

The study will be a single-site, phase 1 clinical trial, with a randomized, blinded (regarding the investigators and laboratory analysts) and crossover design. Two intervention groups will be tested: 1. Rinsing with a fluoride mouth rinse only, based on sodium fluoride at an over-the-counter concentration; 2. Rinsing with the same fluoride mouth rinse as in 1, but after a mouth rinse with calcium lactate (a food additive, previously used to enhance the intraoral fluoride retention [Vogel et al., 2006a; 2006b; 2008a; 2008b; Souza et al., 2016]).

For each volunteer, randomization will be used to determine which of the two intervention groups to be tested first. Volunteers randomized to start the trial in group 1, will test group 2 in the following phase, and vice versa. Dental plaque (primary endpoint) and saliva (secondary endpoint) will be collected for fluoride analysis. Calcium concentration in both samples will also be determined (secondary endpoints).

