5.2 EXCLUSION CRITERIA

An individual who meets any of the following criteria will be excluded from participation in this study:

1. Unable to understand and/or follow study instructions
2. Active periodontitis
3. Oral pain
4. In need of urgent dental care

LIFESTYLE CONSIDERATIONS

During this study, participants are asked to:

- Use a standardized toothpaste and toothbrush, provided by the study team at the first visit, to level the background exposure to fluoride, 7 days prior to each experimental phase
- Refrain from using any other mouth rinse or professional products during the study period
- Refrain from drinking green or black tea (which have high fluoride concentration) on the night before or the day of their visits
- Refrain from brushing their teeth on the night before and the morning of tests/sampling
- Refrain from eating or drinking for 2 hours after the rinses, during which saliva and dental plaque will be sampled

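### The between-person regression of fluoride AUC on salivary flow makes no use of the pre-rinse fluoride already measured, so its slope mixes any resting association with retention of the rinse

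*Combined protocol and SAP*

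**What the plan says.** The objective in Section 3 is to "Determine the role of hyposalivation on the retention of fluoride in the mouth after a fluoride rinse". For this, Section 9.4.1 states: "regression analysis will be used to correlate the data of salivary flow with fluoride concentration (area under the curve of fluoride concentration over time". This covers both saliva and biofilm, and the stated purpose is "to help understand the effect of flow rate on fluoride salivary clearance". It adds: "A significance level of 5% will be used in this analysis". Section 9.1 states the test as beta = 0 against beta not equal to 0, and Section 9.3 includes everyone who completes the fluoride-only rinse.

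A pre-rinse sample exists. Biofilm fluoride "will be determined from the samples collected at baseline and 15 min, 60 min and 120 min" (Section 9.4.2); saliva also has a baseline sample (Section 9.4.3). No section subtracts this value, enters it as a covariate in the flow regression, or relates it to flow. Nor is it stated whether the AUC starts at the pre-rinse or the first post-rinse sample.

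Background is controlled by design only. The lifestyle rules under Section 5.2 require a standard toothpaste and toothbrush "to level the background exposure to fluoride, 7 days prior to each experimental phase". They also rule out other rinses and professional products during the study, tea from the night before, and brushing from the night before.

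**The concern.** In the rinse comparison each participant is a block, so a stable personal fluoride level largely cancels. In the flow regression nothing cancels: each person contributes one AUC, and whatever fluoride was there before the rinse is part of it.

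The protocol gives reason to think resting fluoride could depend on flow. Section 4.1 proposes that "the reduction in saliva flow (hyposalivation) reduces the clearance and therefore increases the retention of fluoride in the mouth"; the same reasoning would apply to toothpaste fluoride. Section 3 justifies the biofilm endpoint by biofilm's capacity to store and slowly release fluoride, and the solid phase is acid-extracted, so earlier deposits are assayed together with rinse fluoride. Equal exposure for seven days does not produce equal resting levels if people clear fluoride at different rates.

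At stake is what a non-zero beta, or a null one, may be said to show. A pre-existing association could be reported as an effect of flow on the rinse, or could hide a real effect of the opposite sign.

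**Working it through.** **The plan's own figures.** The only sample-size figure concerns the rinse comparison: 15 x 1.30 = 19.5, giving 20. The 15 cannot be reproduced because no effect size or SD is given. Nothing is stated for the regression. By Fisher's z with two-sided alpha 0.05 and 80% power, n = 20 detects |r| of about 0.59 and n = 15 about 0.67. The point does not depend on these figures.

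**Decomposition.** Let C0 be the pre-rinse concentration and T the AUC window: 120 min for biofilm and 121 min for saliva if the AUC starts at time zero, or 120 - 15 = 105 and 121 - 16 = 105 min if it starts at the first post-rinse sample. With background stable over the window,

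AUC = incremental AUC + C0 x T.

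A least-squares slope is linear in the outcome, so for the untransformed AUC

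beta(AUC on flow) = beta(increment on flow) + T x beta(C0 on flow).

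The second term existed before the rinse. It vanishes only if C0 is unrelated to flow, and nothing in the plan checks that.

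**Size (all inputs assumed).** The documents give no background level, spread or correlation with flow. Take n = 20, log-SD 0.5 for both background and increment, 15% assay error, decay 0.03/min, the protocol's biofilm sampling times, and an increment independent of flow. Let f be the background share of the AUC and rho the correlation of log background with flow on the scale used. To first order, for log AUC,

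r = f x rho / sqrt(f^2 + (1 - f)^2).

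- f = 0.05, rho = -0.6: -0.03 / 0.951 = -0.03 (simulated -0.04).
- f = 0.25, rho = -0.6: -0.15 / 0.791 = -0.19 (simulated -0.19).
- f = 0.50, rho = -0.6: -0.30 / 0.707 = -0.42 (simulated -0.39).

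Rejection rate of beta = 0 at two-sided 5%, 20,000 simulated trials per cell, uncorrected log AUC:

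| Background share | rho -0.3 | rho -0.6 | rho -0.8 |
|---|---|---|---|
| 5% | 5.1% | 5.5% | 5.4% |
| 10% | 5.3% | 6.0% | 6.9% |
| 25% | 7.2% | 13.4% | 21.3% |
| 50% | 13.6% | 43.9% | 71.3% |

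Saliva times give nearly the same. For shares up to 50% in biofilm, the incremental AUC rejects in 4.9-5.6%, and log AUC with log baseline as covariate in 4.7-6.5%. At a 75% share with rho = -0.8 these rise to about 7% and 12%.

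**A second model.** Ten people have flow 0.02-0.1 and ten 0.1-0.6 mL/min. Background is proportional to flow^-0.25 or flow^-0.5 with log-SD 0.5; rinse AUC has log-SD 0.4 and does not depend on flow. The uncorrected test rejects in about 5% at a 5% share, 8-22% at 20% and 27-75% at 50%. A slightly different scaling of background gives 8-17% at 20% and 28-68% at 50%. With correction (20% baseline error) it is 4-5%.

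**Masking.** In that model, let low flow truly lower rinse fluoride (rinse AUC proportional to flow^0.25). At a 30% share, power is about 62% corrected, against 24% or 8.5% uncorrected for the two background exponents.

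**Price of correcting.** Let flow act on both sources in the same direction (exponent -0.25). Detection falls from 79% to 57% at a 30% share, and from 78% to 45% at 50%.

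**The case against.** Several points on the other side carry weight.

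- **The zero-effect null is strained.** If slow clearance raises resting fluoride, it should raise rinse fluoride too; beta is then truly non-zero and rejecting is right. This stands against reading the rejection rates above as the trial's false-positive rate. It does not remove the extra term in the slope.
- **The planned outcome matches the stated endpoint.** Sections 3 and 9.1 speak of fluoride concentration after a rinse, not of an increment. This stands: the uncorrected AUC is a legitimate quantity and should stay. The objective and the aim of understanding clearance, however, concern what happens to the rinse.
- **Design controls do more than level toothpaste.** No brushing, tea or other rinses shortly before sampling should lower background. This stands, and largely answers the remark in Section 2.2 that "higher fluoride concentration products are usually recommended for older adults with hyposalivation". Lower background is not background unrelated to flow.
- **Correction has costs.** Each biofilm sample comes from a different quadrant, so one baseline reading is noisy. If up to 3% of increments fall at or below zero, up to 1 - 0.97^20 = 46% of 20-person trials would have at least one, and those values cannot be log-transformed. This argues against replacing the planned AUC.

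A reader might also infer that the bias favours the Section 4.1 hypothesis. The documents do not support that: Section 2.1 expects low calcium at low flow to reduce retention, and this could apply to background as well.

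**Conclusion.** The gap is real. As written, the flow regression cannot separate an association that existed before the rinse from an effect of flow on rinse fluoride, and the sample that would separate them goes unused for this purpose. Beta may be inflated or masked; neither direction nor size can be settled from the documents.

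Under the assumptions shown, the distortion is negligible when background is about 5% of the AUC and becomes material from about 20-25% upward if background is strongly related to flow. The figures at a 50% share are illustrations, not estimates for this trial, and they also assume that flow does not act on rinse fluoride.

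The point is confined to the flow analysis, which Section 3 labels exploratory although the synopsis lists its objective as the only secondary one. It should not be extended to the primary rinse comparison, which is within person and largely protected.

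**What to change.** In Section 9.4.1, keep the planned AUC regression, state where the AUC starts, and pre-specify beside it:

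1. a regression of pre-rinse fluoride at the fluoride-only visit on salivary flow;
2. a baseline-corrected flow regression for saliva and for each biofilm phase, using the incremental AUC above the participant's own pre-rinse value, analysed untransformed. Where increments can be at or below zero, use instead the AUC with log pre-rinse fluoride as a covariate.

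Add that a flow effect will be attributed to retention of the rinse only if the corrected analysis supports it.

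The cost is a few sentences. The pre-rinse samples are already collected and assayed at each treatment visit, so no visit, sample or assay is added. The drawback is noise from the single pre-rinse reading, taken from a different quadrant for biofilm, and lower power when flow moves background and rinse fluoride in the same direction. Reporting both results lets the reader see this.
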